### **Safety assessment**

- Presence and nature of adverse events during the therapy, their association with the drug administration and other features.

---

 Temperature scoring to determine total disease score will be made at the statistical analysis by OOO “NPF “Materia Medica Holding” personnel. To do this, absolute body temperatures (in degrees Celsius) will be converted to points (or scores) using the following scale:  $\leq 37.2^{\circ}\text{C}$ =0 points;  $37.3\text{-}38.0^{\circ}\text{C}$ =1 point;  $38.1\text{-}39.0^{\circ}\text{C}$ =2 points;  $\geq 39.1^{\circ}\text{C}$ =3 points.

## **Study design**

Study design: an open-label, comparative, randomized, parallel group clinical study to evaluate efficacy of the study treatment.

The study will enroll outpatient subjects of either gender aged 18-70 years old inclusively with clinical manifestations of influenza during seasonal morbidity seeking medical advice within the first two days of the disease.

After signing informed consent to participate in the clinical study baseline examination will be initiated including nasal swab for rapid diagnosis and verification of influenza as the cause of the disease. In case of positive result of immunochromatographic test the patient will be enrolled. In case of negative result of rapid test the patient will be enrolled provided that (1) he/she has clinical manifestations of typical influenza; (2) the history evidences contact with a patient with influenza; (3) the region has influenza epidemics. Additionally, at the screening (Day 1) all patients regardless of the results of rapid test will provide nasopharyngeal swabs for further PCR diagnosis and identification of RNA of influenza A and B virus, thermometry, history collection, evaluation of vital signs, physical examination will be performed and concomitant therapy will be recorded. Females of childbearing potential will undergo pregnancy test. If inclusion criteria are met and non-inclusion criteria are absent (Day 1) the patient will be enrolled in the trial and randomized into one of the two groups: group 1 will receive Ergoferon as per the selected dosing regimen for 5 days; group 2 will be treated with Oseltamivir at 75 mg twice a day for 5 days.

At Day 1 visit the patient will receive the study product and an antipyretic product approved by the study protocol.

The patient will receive the diary in which he/she will have to record axillary body temperature (measured by non-mercuric Geratherm Classic thermometer ) in the morning and evening as well as intensity of the disease symptoms and number of doses of the antipyretic product. The investigator will train the patient concerning the diary filling.

In total 3 visits (Days 1, 3 and 7) will be made by the patient/investigator during the treatment and follow-up period, on day 5 an additional visit will be made for nasopharyngeal swabs.

At Day 1, Day 3 and Day 7 visits blood sampling will be made for immunological tests at the investigator's discretion. At Day 3 and Day 7 visits the investigator will collect complaints, document examination findings, intensity of influenza symptoms in scores, control the prescribed and concomitant medications, assess safety of the study therapy and check the patient's diary. Furthermore, nasopharyngeal swabs (Days 1, 3, 5, 7) and blood samples (Days 1, 3, 7) will be made for lab tests. The total observation period will be 7 weeks (screening, randomization – 1 day, treatment – 5 days, follow-up – 2 days). The patient will keep diary throughout the whole 7-day observation period.

Symptomatic therapy of influenza and co-morbidities will be allowed except for the products specified in “Forbidden concomitant therapy” section.

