## Protocol Summary

This document represents the protocol summary for the study on human subjects. The study will be carried out in accordance with ICH GCP, National Standard of the Russian Federation GOST 52379-2005 "Good Clinical Practice", Helsinki Declaration of World Medical Association, relevant requirements of the regulatory authorities as well as the study procedures.

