## **Inclusion and exclusion criteria**

### ***Inclusion criteria***

1. Patients aged from 18 to 70 years.
2. Patients who were admitted to hospital within 48 hours from the onset of influenza signs.
3. Patients with body temperature  $\geq 37.8^{\circ}\text{C}$  when visiting a doctor + severity of influenza symptoms  $\geq 4$  scores (presence of at least one general symptom  $\geq 2$  scores and 1 nasal/throat/chest symptom  $\geq 2$  scores or greater number of symptoms with the severity  $\geq 1$  point).
4. Diagnosed influenza confirmed by rapid diagnostic test (OSOM Influenza A&B Test).
5. The possibility to start therapy after the onset of the first symptoms of influenza.
6. Usage of contraceptive methods by both gender patients of reproductive age during the trial and within 30 days after ending the participation in the trial.
7. Availability of signed patient information sheet (Informed Consent form) for participation in the clinical trial.

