### **Discontinuation criteria**

1. Participant's failure or decline to comply with the protocol requirements.
2. Deviation from the schedule of examinations and sampling for lab tests by  $\geq 1$  day.
3. The necessity to use medications not permitted in the study.
4. An adverse event requiring discontinuation of the study drug.
5. Patients who decide to withdraw early from the study due to lack of treatment efficacy or for any other reason.

6. Cases not stipulated in the protocol where the investigator decides that further participation may harm the patient.
7. Eligibility error.

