### **Number of patients**

198 Informed consent forms are supposed to be signed and expected to yield at least 158 patients (79 x 2 groups (Ergoferon and Oseltamivir)) completing all the protocol procedures (withdrawal index 1,2).

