## Statistical Analyses

### *Samples*

Total set comprised all enrolled patients whose parents/adopters had signed the informed consent form for participation of a patient in the trial. This sample will consider all adverse events throughout the study, including those occurred prior to the study therapy. Any medically unfavourable events (conditions) recorded in patients from Total set after signing informed consent but before administration of the study product will be considered as concomitant conditions.

Sample of the patients receiving at least one dose of the study product will be used for the study drug safety assessment (Safety population), as any adverse events emerging after administration of the product will be recorded.

Full Analysis Set This sample will consist of all enrolled patients, except for those who met at least one of the following criteria:

- 1) failure to meet inclusion/non-inclusion criteria;
- 2) patient failing to take any dose of the study drug;
- 3) absence of any data on the patient after randomization.

This was the best set for the Intention-to-treat method, so it will be used in the Intention-to-treat efficacy analysis of the test therapy.

Unavailable/missing data (parameters/variants) will be completed by the Last Observation Carried Forward method (LOCF).

Per Protocol set. This sample includes all patients who completed the therapy as per the study protocol, without any missing visits or major protocol deviations. This set will be used in the Per Protocol efficacy analysis of the test therapy.

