1.8 where  $N_F$  – final sample size;  $N$  – result of calculation in cl. 1.6, i.e. scheduled number of patients completing the study per protocol;  $C_w$  – withdrawal coefficient.

2. Assumptions on expected clinical study effects:

2.1 The difference between proportions of the patients with recovery/improvement on days 2-7 (according to the patient’s diary) and on days 3 and 7 (according to objective medical examination) in Ergoferon group and Oseltamivir is expected to be  $\geq 0\%$ .

The minimum size of each group will be determined as follows:

Number of patients	Final analysis
Number of patients in both groups	158
including	
- number of patients in Ergoferon groups	79
- number of patients in Oseltamivir group	79

Taking into account that potential withdrawal of 20% patients during the screening and during the study, at least 198 patients (99 in Ergoferon and Oseltamivir group) should sign informed consent.

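### The design section enrols some rapid-test-negative patients whom inclusion criterion 4 rules out, and nothing says how such a patient, if randomised, counts in the full analysis set

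*Combined protocol and SAP*

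**What the plan says.** The Study design section of the combined protocol and SAP describes what follows the rapid test. A positive result leads to enrolment. For the other case it says: "In case of negative result of rapid test the patient will be enrolled provided that" three conditions are met jointly, namely a typical clinical picture, a history of contact with an influenza patient, and an epidemic in the region. Every patient also gives a day-1 swab for PCR, whatever the rapid test shows.

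Inclusion criteria, item 4, reads: "Diagnosed influenza confirmed by rapid diagnostic test (OSOM Influenza A&B Test". It offers no alternative route and does not refer back to the design section. Later in the Study design section comes a general condition: "If inclusion criteria are met and non-inclusion criteria are absent (Day 1) the patient will be enrolled in the trial".

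Two other rules depend on eligibility. Discontinuation criteria, item 7, is "Eligibility error". In the Samples section, the first ground for leaving the FAS is "failure to meet inclusion/non-inclusion criteria". The FAS is the set named for the intention-to-treat efficacy analysis.

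On numbers, the Number of patients section states: "198 Informed consent forms are supposed to be signed and expected to yield at least 158 patients". The Evaluation of sample size section bases this on "potential withdrawal of 20% patients during the screening and during the study".

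**The concern.** An investigator who follows the design section will enrol certain rapid-test-negative patients. One who follows the numbered criteria will turn the same patients away. Sites could therefore recruit different populations under one protocol.

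The conflict also reaches the analysis, because eligibility decides membership of the FAS. A patient enrolled exactly as the design section directs may later be kept or dropped, and the text supports either choice. The trial is open-label and the document does not say when the analysis sets are fixed, so nothing in it prevents that classification from being made once outcomes are known. For a non-inferiority comparison whose stated purpose is the treatment of influenza, who counts as having influenza should not be left open.

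**Working it through.** **1. The two rules side by side**, for a rapid-test-negative patient who meets the three conditions:

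| Stage | If the design-section route governs | If criterion 4 governs |
|---|---|---|
| Screening | Enrolled | Screen failure |
| If randomised | Valid participant | Eligibility error, a listed ground for discontinuation |
| FAS | Kept, given at least one dose and some post-randomisation data | Removed under the first FAS exclusion |

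The columns differ in every row, and no section gives an order of precedence. The later sentence in Study design ("If inclusion criteria are met and non-inclusion criteria are absent (Day 1) the patient will be enrolled in the trial") does not settle the matter, because it sets that section against its own negative-test route. The day-1 PCR result does not settle it either: the document gives it no role in eligibility or in any analysis set.

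**2. When the FAS is affected.** If criterion 4 is applied strictly at screening, these patients never enter any set. The FAS classification becomes ambiguous only if at least one of them is randomised. The design section provides for that, but the document gives no expected number.

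**3. The plan's own allowance.** Inputs: 158 completers (79 per group) and 20% losses, covering both screening and the study.

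- Consents: 158 / (1 − 0.20) = 197.5, rounded up to 198. The stated figure reproduces.
- Losses the plan can absorb: 198 − 158 = 40, and 40/198 = 20.2%.

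**4. What criterion 4 would cost.** Let w be the share of other losses among those who pass screening (an assumption; the document does not split the 20%). Rapid-test screen failures that still leave 158 completers = 198 − 158/(1 − w).

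- w = 10%: 198 − 175.6 = 22.4, so 22 (11% of consents).
- w = 5%: 198 − 166.3 = 31.7, so 31 (16% of consents).

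Beyond that point power falls. As an illustration, 20% screened out and 10% other losses leave 198 × 0.8 × 0.9 = 142.6, about 71 per arm. Take power = Φ(0.20/√(2p(1−p)/n) − z), with the 20-point margin, a true difference of zero and a common recovery proportion p. The document does not state p, so two values are used, each of which gives roughly the planned 80% at n = 79:

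- one-sided 5%, p = 0.50: 81% at n = 79, 77% at n = 71;
- two-sided 5%, p = 0.722: 80% at n = 79, 76% at n = 71.

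**5. Direction of any bias under the design-section route.** Let f be the share of FAS patients without influenza, D the Ergoferon deficit in influenza patients and d the deficit in the others. The average deficit is D(1 − f) + d·f = D − f(D − d). With assumed D = 20 points and f = 20%:

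- d = 0: 20 − 0.2 × 20 = 16 points, a shift favouring non-inferiority;
- d = 20: 20 points, no shift;
- d = 30: 20 + 0.2 × 10 = 22 points, a shift against non-inferiority.

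None of f, D and d is in the document. Moreover, f is not the share with a negative rapid test. A rapid-test-negative patient may have influenza and a positive one may not, and no test accuracy is given to link the two.

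**The case against.** The best defence is that criterion 4 is shorthand for the design-section rule. The document says of itself: "This document represents the protocol summary for the study on human subjects". The design section is the more specific text, with three joint conditions and a PCR swab for everyone, so the intended reading may be clear to the sponsor. This supports treating the matter as a wording repair. It does not remove the conflict: criterion 4 names the test as the means of confirmation, a negative result cannot confirm, and both rules stand in the same summary.

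Three stronger readings are tempting, and the document supports none of them.

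- *That two different full analysis sets necessarily result.* This needs at least one rapid-test-negative patient to be randomised.
- *That the trial is biased towards non-inferiority.* Step 5 shows that the direction depends on unknown quantities. The three conditions, the symptom threshold in inclusion criterion 3 and exclusion criterion 3 (suspected look-alike diseases) all limit how many patients without influenza could enter.
- *That applying criterion 4 leaves the trial underpowered.* The 20% allowance already covers screening. Also, 79 per arm is a count of completers, and the FAS does not require completion, so it could be larger.

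It is also fair to say that post hoc classification is only a possibility, and that an analysis missing from a summary is weak evidence that none is planned.

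**Conclusion.** The point stands as an internal inconsistency in the eligibility rule that carries through to discontinuation and the FAS. It rests on the wording alone and needs no assumption. It has to be corrected, because sites and analysts cannot follow both rules.

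No effect size is claimed. The power figures above are conditional illustrations: they show that criterion 4 costs nothing until total losses pass 40 of 198, and about four percentage points in the example that goes beyond it.

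**What to change.** **Required.** Reconcile the Study design section, Inclusion criteria item 4, Discontinuation criteria item 7 and the FAS definition in Samples. The result should be one eligibility rule and one stated FAS classification for rapid-test-negative patients, fixed before outcome data are seen. Which rule to adopt is for the sponsor. The cost is wording. If criterion 4 is kept, more patients need to be screened only if screen failures and other losses together are expected to exceed the planned 20%.

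**Optional, using swabs already planned for everyone on day 1.**

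- Report the non-inferiority comparison in patients PCR-positive on day 1, with its confidence interval, as a supporting analysis and not a gate. The swab is taken at screening, so the subset is defined before treatment. The downside is lower precision. If, by assumption, 20% of 79 per arm were not PCR-positive, 79 × 0.8 = 63.2 per arm would remain. Power by the formula above would then be 73% against 81% (one-sided 5%, p = 0.50) or 71% against 80% (two-sided 5%, p = 0.722).
- Restrict secondary outcome 10 (negative virology on days 3, 5 and 7) to patients PCR-positive on day 1, so that those negative at baseline do not count as later negatives.

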## Study purposes

- To assess the efficacy of Ergoferon in the treatment of influenza.
- To compare the efficacy of Ergoferon and Oseltamivir in the treatment of influenza.
- To assess the safety of Ergoferon in the treatment of influenza.

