### *Evaluation of sample size*

The sample size was assessed in accordance with the following rules and assumptions:

1. Statistical assumptions:

- 1.1 Lack of clinically relevant superiority of reference product (oseltamivir) over test product (Ergoferon) is assumed, thus statistically meeting Non-Inferiority design:

$$\mathbf{H_0: Ef_{control} - Ef_{test} \geq \delta}$$

$$\mathbf{H_A: Ef_{control} - Ef_{test} < \delta,}$$

where  $\mathbf{Ef_{control}}$  – effect of reference product (oseltamivir),  $\mathbf{Ef_{test}}$  – effect of test product (Ergoferon),  $\delta$  – clinically relevant difference;

- 1.2 Clinically relevant difference value “ $\delta$ ” is considered to be equal to 20% (i.e. Ergoferon effect is supposed to be comparable to the one of oseltamivir if the effect of test product is superior to or inferior to the effect of reference product by no more than 20%);
- 1.3 The power of statistical tests ' $P = (1 - \beta)$ ' is 80% (the probability of correct rejection of the null hypothesis is 0.8);
- 1.4 The probability of type 1 error ' $\alpha$ ' is less than 5% (the probability of false acceptance of the alternative hypothesis is less than 0.05);
- 1.5 Therefore, sample size will be calculated taking into account:
- a. assumption on expected effects declared in the main efficacy criterion of the protocol;
- 1.6 calculation of sample size of groups 1 and 2 for two-sided test for final analysis will be made using the formula:

$$\mathbf{N_1=N_2=(p_a(1 - p_a) + p_b(1 - p_b)) I,}$$

where  $\mathbf{N_1}$  and  $\mathbf{N_2}$  – samples sizes in Ergoferon and Oseltamivir groups

$\mathbf{p_a}$  and  $\mathbf{p_b}$  – expected proportions of the patients with recovery/improvement in these groups

$\mathbf{I}$  – Fisher's information detected using the formula:

$$\mathbf{I=(z_\alpha + z_\beta)^2/(\theta - \delta)^2,}$$

where  $\mathbf{z_\alpha}$  and  $\mathbf{z_\beta}$  – tabular values of z-test for  $\alpha$  and  $\beta$ ,  $\theta$  – difference between proportions ( $\mathbf{p_a - p_b}$ ),  $\delta$  – clinically relevant difference;

- 1.7 final sample size will be determined using the formula:

$$\mathbf{N_F = N / (1 - K_B),}$$

---

 SAS/STAT(R) 9.2 User's Guide, Second Edition.

[http://support.sas.com/documentation/cdl/en/statug/63033/HTML/default/viewer.htm#statug\\_seqdesign sect027.htm](http://support.sas.com/documentation/cdl/en/statug/63033/HTML/default/viewer.htm#statug_seqdesign sect027.htm)

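### The Day 1 influenza PCR taken from every patient defines no efficacy set, so PCR-negative patients stay in the non-inferiority comparison and, if they respond alike in both arms, shrink a true deficit

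*Combined protocol and SAP*

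**What the plan says.** **Target.** The second study purpose is "To compare the efficacy of Ergoferon and Oseltamivir in the treatment of influenza". The other two, on the efficacy and safety of Ergoferon, also refer to influenza.

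**Entry.** Study design enrols patients with a positive rapid test. It also opens a second route: "In case of negative result of rapid test the patient will be enrolled provided that" three conditions hold (typical clinical picture, contact history, regional epidemic). Inclusion criterion 4 reads differently: "Diagnosed influenza confirmed by rapid diagnostic test (OSOM Influenza A&B Test". PCR is not an entry criterion in either place.

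**PCR.** At baseline, "all patients regardless of the results of rapid test will provide nasopharyngeal swabs for further PCR diagnosis and identification of RNA of influenza", with types A and B as the targets. Study design places this swab at screening, before randomisation and treatment. Apart from that baseline swab, PCR serves efficacy only through secondary outcome 10 (negative virology on days 3, 5 and 7), which is not limited to patients positive on Day 1.

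**Analysis sets (Samples).** For the Full Analysis Set: "This sample will consist of all enrolled patients, except for those who met at least one of the following criteria". The three criteria are "failure to meet inclusion/non-inclusion criteria", no dose taken, and no data after randomisation. For the Per Protocol set: "This sample includes all patients who completed the therapy as per the study protocol, without any missing visits or major protocol deviations". Neither definition mentions PCR, and Statistical Analyses contains no PCR-based subgroup or sensitivity analysis.

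**Hypothesis (Evaluation of sample size, item 1.1).** "Lack of clinically relevant superiority of reference product (oseltamivir) over test product (Ergoferon) is assumed, thus statistically meeting Non-Inferiority design". The margin is 20%, power is 80% and alpha is below 5%. The sample-size formula is described as being for a two-sided test, with 79 completers per group.

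**The concern.** The claim to be supported is about influenza, but the analysed population is defined by a rapid test or, under Study design, by clinical and epidemiological grounds. The plan collects a pre-treatment measurement that would show which patients had detectable influenza RNA, then does not use it to define any efficacy population.

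The direction matters because this is a non-inferiority comparison. In a superiority trial, patients in whom the arms do not differ make success harder. Here they make it easier: if the test product is worse in influenza, including patients with no arm difference moves the observed deficit away from the margin. Comparing Full Analysis Set and Per Protocol results would not reveal this, because neither definition removes a patient for a negative Day 1 PCR. Secondary outcome 10 has a related weakness, since a patient already negative on Day 1 can count as a virological success in either arm.

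**Working it through.** **Inputs from the plan.** Margin δ = 0.20, power 0.80, alpha 0.05 with a two-sided test, expected true difference taken as 0 (stated as at least 0%), and 79 per group.

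**Inputs not in the plan (assumptions).** The response rates p_a and p_b; the PCR-negative share f; equal response in both arms among PCR-negative patients.

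**Step 1: the plan's own figure.** The formula is N = [p_a(1−p_a) + p_b(1−p_b)]·(z_α + z_β)²/(θ − δ)². Because the rates are not stated, 79 cannot be reproduced from stated inputs alone. Solving backwards with z_α = 1.96, z_β = 0.842, θ = 0 and equal rates:

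- (1.960 + 0.842)² = 7.849, and 7.849/0.04 = 196.2.
- 79 = 2p(1−p) × 196.2, so p(1−p) = 0.2013 and p ≈ 0.72 (or 0.28).

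I use 0.72 as the control rate. A one-sided 0.05 test with p = 0.50 gives 78, so the plan's intended inputs remain uncertain. The stated inflation does reproduce: 79/(1 − 0.20) = 98.75, rounded up to 99 per group and 198 in total.

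**Step 2: dilution.** With share f in both arms and no arm difference among PCR-negative patients, observable deficit = (1 − f) × deficit in influenza patients. Set the true deficit at exactly 20 points (72% against 52%), so that the null hypothesis is true in influenza patients.

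**Step 3: chance of falsely concluding non-inferiority.** P = Φ[(0.20 − observable deficit)/SE − 1.96], where SE = √{[c(1−c) + t(1−t)]/79}, and c and t are the mixed response rates in the two arms. PCR-negative patients are given a 72% response in both arms, so c = 0.72 and t = 0.52 + 0.20f. Example at f = 0.20: t = 0.56, SE = 0.0753, (0.20 − 0.16)/0.0753 = 0.531, and Φ(0.531 − 1.960) = 7.7%.

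| PCR-negative share | Observable deficit (points) | False non-inferiority |
|---|---|---|
| 0% | 20 | 2.5% |
| 2% | 19.6 | 2.8% |
| 5% | 19 | 3.4% |
| 10% | 18 | 4.5% |
| 20% | 16 | 7.7% |
| 30% | 14 | 12% |
| 40% | 12 | 19% |

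Giving PCR-negative patients a 52% response in both arms changes little: 4.5%, 7.5%, 12% and 18% at shares of 10%, 20%, 30% and 40%. If one-sided 0.05 was intended, the baseline is 5%, rising to about 8%, 13%, 19–20% and 26–28% at the same shares (control rate 60–72%).

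**Step 4: which shares are relevant.** The two entry texts lead to different populations.

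- Under Study design, rapid-negative patients may enter, and rapid-positive patients may be PCR-negative. Both routes contribute to f.
- Under inclusion criterion 4, a rapid-negative patient fails an inclusion criterion and is removed by the first Full Analysis Set exclusion. Only false-positive rapid tests contribute to f.

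The plan gives no figure for either route.

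**Step 5: precision of a PCR-confirmed set.** With 79(1 − f) patients per arm, both rates 72% and true difference 0, power = Φ[0.20/√(2 × 0.72 × 0.28/(79(1 − f))) − 1.96]. This is about 80% at f = 0, then 76%, 71%, 65% and 58% at f = 10%, 20%, 30% and 40%.

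**The case against.** **Criterion 4 may remove most of the problem.** Study design itself enrols only patients who meet the inclusion criteria, and eligibility error is a discontinuation criterion. If criterion 4 governs, rapid-negative patients leave the Full Analysis Set. With a small false-positive share the inflation is modest: 2.8% at 2% and 3.4% at 5%, against 2.5%. This stands as a limit on size. It does not close the gap, because a rapid-positive, PCR-negative patient is kept under either reading.

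**Equal response is a premise.** The documents do not show that the arms respond alike in non-influenza illness, and the listed active ingredients of Ergoferon (antibodies to interferon-gamma, histamine and CD4) are not influenza-specific. This stands. The shrinkage is conditional on that premise, and it favours non-inferiority only if Ergoferon is worse in influenza.

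**Silence is weaker evidence in a summary.** The document calls itself a protocol summary, and it does not define which deviations are major for the Per Protocol set. So the supportable statement is that no PCR-based set is stated here. Exclusion criterion 3 does not fill the gap: it concerns other illnesses suspected at entry, not a PCR result that comes later.

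**A stronger remedy would be costly.** Requiring success in both sets would lower overall power, at a true difference of 0, from about 80% to about 74%, 68%, 63% and 56% at PCR-negative shares of 10%, 20%, 30% and 40%. This stands, and such a rule is not needed to address the point.

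**Conclusion.** The point holds as a gap in the analysis plan whose size is unknown. The plan makes a claim about influenza, measures influenza by PCR in everyone before treatment, and states no efficacy set that uses the result. If PCR-negative patients respond alike in both arms, a 20-point deficit in influenza patients appears as 20(1 − f) points. False non-inferiority then rises from 2.5% to between about 2.8% (f = 2%) and 19% (f = 40%), assuming a 72% control rate, 79 per arm and a two-sided 95% interval.

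A reader might infer that the comparison is certainly and substantially biased toward no difference. The documents do not support that: they give no PCR-negative share, no response rates and no evidence on arm differences outside influenza, and inclusion criterion 4 may confine the problem to false-positive rapid tests. A reader might also infer that non-inferiority should be claimed only if both sets succeed. That is an option, but nothing in the plan makes it necessary, and the power loss is material.

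**What to change.** 1. Under Samples, define a PCR-confirmed set: randomised patients whose Day 1 nasopharyngeal swab is PCR-positive for influenza A or B. The swab precedes treatment, so selecting on it keeps the randomised comparison.
2. Pre-specify the primary non-inferiority comparison in this set as a key supportive analysis. Report it beside the Full Analysis Set with its estimate and confidence interval, and give the PCR-negative share by arm. Word any conclusion about influenza in light of both results. Because the trial is open-label, fix this before outcomes are examined.
3. Reconcile the enrolment text in Study design with inclusion criterion 4, and state how the outcome applies to the first Full Analysis Set exclusion.

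**Cost.** The swabs are already planned, so items 1 and 2 need wording and one further run of the primary analysis. The interval in the confirmed set will be wider, with the power loss shown in step 5 of the working. No enlargement is needed for a supportive analysis. If the sponsor wanted 79 confirmed completers per arm, consents would rise from 198 to 2 × ⌈79/((1 − f) × 0.8)⌉, which is 220, 248, 284 or 330 at PCR-negative shares of 10%, 20%, 30% or 40%.
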